Life threatening: any adverse drug experience that places the patient or subject, in the view of the investigator, at immediate risk of death from the reaction as it occurred, i.e., it does not include a reaction that had it occurred in a more severe form, might have caused death.

Changes in the severity of an AE will be documented to allow an assessment of the duration of the event at each level of intensity to be performed. We will document the duration of each episode characterized as intermittent.

Relationship to Study Products, Study Procedures and Initial UTI: The clinician’s assessment of an AE’s relationship to the study product, study procedures and initial UTI is part of the documentation process, but it is not a factor in determining what is or is not reported in

the study. If there is any doubt as to whether a clinical observation is an AE, the event will be reported. All AEs will have their relationship to study product assessed using the terms: related or not related. In a clinical trial, the study product must always be suspect. To help assess, the following guidelines will be used.

- Related – There is a reasonable possibility that the study product caused the adverse event. Reasonable possibility means that there is evidence to suggest a causal relationship between the study product and the adverse event.
- Not Related – There is not a reasonable possibility that the administration of the study product caused the event.

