4.2.6 Safety Analysis

Safety will be evaluated by the collection and analysis of data on (S)AEs. All (S)AEs will be reported, regardless of their relationship to study product (*Table 24 in Section 7.1*). The number of subjects with adverse events and the number of adverse events will be reported by body system and by treatment arm (*Table 24A-B in Section 7.1*). (S)AEs results (the number of subjects with adverse event and the number of adverse events) will be compared by treatment arm, with statistical tests for differences in proportion of subjects with serious adverse events between study arms. These analyses will use the ITT population and two-sided tests with significance level of 0.05 (*Table 25A in Section 7.1*).

Missing Data: Initially we will assess the extent and pattern of missing data using frequencies and cross-tabulations. If data are missing for only a few cases (5% or less), then data analysis will be conducted only on study participants with complete data. However, when such a strategy would result in loss of data from a substantial proportion of participants (i.e., 20%) or would lead to biased or inaccurate results, then sensitivity analysis or some form of imputation will be performed. The form of

imputation used will depend on the nature of the data that are missing. If data are missing for primary endpoint (treatment failure), frequencies for missing data by center, patient characteristic (clinical and demographic), and medication used will be examined. If there are significant associations of missingness with any of these characteristics, we would consider intent-to treat analysis with imputation methods such as regression technique, hot-deck, or best/worst case (for binary outcomes) and choose the one that would be most appropriate for type of missing data pattern (missing at random). If there is partial follow-up, that partial data might allow us to do an imputation. The imputation will be employed if there is a clear evidence of bias due to missing data. Sensitivity analyses will be performed to assess how sensitive results are to reasonable changes in the assumptions that are made for missing data.

To be considered evaluable a child must meet (a) below and one of (b) , (c) or (d):

(a) have taken study medication, AND;

(b) complete the Test of Cure visit, OR;

(c) have prior evidence of a treatment failure;

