	Arm 1: Standard Course Total= xxx N (%)	Arm 2: Short Course Total= xxx N (%)	p -value
Total number of subjects with AEs			
Total number of Adverse events			
Number of AEs per patient			
0			
1			
2			
3+			
Severity of AE			
Mild			
Moderate			
Severe			
Serious adverse events			
Yes			
No			
Relationship to medication			
Related			
Not related			
Outcome			
Recovered/Resolved			
Unchanged			
Ongoing			
Yes			
No			

Specifications

- Restrict the analysis to population 1 separately by number of subjects with adverse event(s) (Table 24A) and number of adverse events (Table 24B).

The test for independence of AE among two arms can be obtained using Chi-square test (or Fisher test if any cell expected count is less than 5).

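### The SAP's adverse-event table does not fix the unit of analysis: event counts may be tested by chi-square as if independent, and the life-threatening grade has no severity row

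*SAP*

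**What the plan says.** SAP 4.2.6 (Safety Analysis) says of the adverse-event results that "the number of subjects with adverse event and the number of adverse events) will be compared by treatment arm". The sentence then continues "with statistical tests for differences in proportion of subjects with serious adverse events between study arms". The tests are two-sided at 0.05 in the ITT population.

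The Table 25 shell in SAP 7.1 has a p-value column with no restriction on which rows it serves. Some rows plainly count children: subjects with AEs, and "Number of AEs per patient" in the categories 0, 1, 2 and 3+. One row plainly counts events: "Total number of Adverse events". The severity, serious-event, relationship, outcome and ongoing rows do not state their unit.

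The specification below the shell reads "Restrict the analysis to population 1 separately by number of subjects with adverse event(s) (Table 24A) and number of adverse events (Table 24B", and then names the method: "The test for independence of AE among two arms can be obtained using Chi-square test", with Fisher's test if an expected count is below 5. No other method for adverse events appears in the SAP.

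The severity rows of Table 25 are Mild, Moderate and Severe. After those three levels, protocol 10.2.1 gives a fourth: "Life threatening: any adverse drug experience that places the patient or subject, in the view of the investigator, at immediate risk of death".

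**The concern.** Chi-square and Fisher tests assume that the counted units are independent. Children are; several events in one child generally are not. A child prone to side effects may report more than one, and their grades and outcomes may be alike. The shell foresees repeats but gives no rule for handling them.

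A programmer who follows SAP 4.2.6 and the Table 25 specification literally would test the event totals, and probably the severity, relationship and outcome rows as well. Protocol 10.2.1 requires each event to be graded, and the Table 24 listing carries severity, relationship and outcome per event. Event totals have a further difficulty: they have no natural denominator. The column layout (a total, then N and %) invites the number of children as denominator, which is wrong for a count that can exceed one per child.

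The stake is the reading of the safety results. Protocol 2.3.2 lists fewer antibiotic side effects as a possible benefit of the short course, so a small p-value in this table could be read as evidence for or against that benefit. Separately, a life-threatening event has no severity row and would have to be merged into Severe or left out of that block.

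**Working it through.** **Inputs.** From the documents: two-sided 0.05 (SAP 4.2.6), and 336 evaluable children per arm (672 at 1:1, protocol section 5). The SAP's own target is 326 per arm, which makes no material difference here. The documents give no adverse-event rate, no events per child and no measure of clustering, so there is no stated figure to reproduce. Everything marked assumed below is an assumption.

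**1. Event totals split 50:50.** Let *D* be the variance of a child's event count divided by its mean. The chi-square test takes *D* = 1. If the true ratio is *D*, the statistic is inflated by *D*, and the real two-sided error is 2 × [1 − Φ(1.96/√*D*)].

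| assumed *D* | 1.96/√*D* | formula | simulated (10,000 runs, mean 0.1, 0.3 or 0.6 events per child) |
|---|---|---|---|
| 1 | 1.960 | 0.050 | 0.046–0.049 |
| 1.5 | 1.600 | 0.110 | 0.102–0.112 |
| 2 | 1.386 | 0.166 | 0.164–0.168 |
| 3 | 1.132 | 0.258 | 0.253–0.261 |

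For scale, take a negative binomial count with assumed mean 0.3. The share of children with no event is *D*^(−0.3/(*D*−1)). At *D* = 2 this is 2^(−0.3) = 0.812, so 18.8% of children have an event, averaging 0.3/0.188 = 1.6 events each. At *D* = 1.5 it is 21.6% of children with 1.39 events each; at *D* = 3, 15.2% with 1.97 each.

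**2. Event totals over number of children.** With mean μ events per child, the 2×2 test uses variance proportional to μ(1 − μ), while the true variance is *D*μ. The error is 2 × [1 − Φ(1.96 × √((1 − μ)/*D*))].

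- *D* = 1 (no clustering), μ = 0.1, 0.3, 0.6: 0.063, 0.101, 0.215 (simulated 0.062, 0.097, 0.221).
- *D* = 2: 0.189, 0.246, 0.381 (simulated 0.190, 0.247, 0.385).

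This layout fails even when events are independent.

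**3. Severity rows, if counted by event.** A 2×3 chi-square was simulated with assumed mean 0.3 events per child, *D* of 1 or 2, and a 60/30/10% grade mix (3,000 runs). The false-positive rate is 0.047 if grades within a child are unrelated. It is 0.060 (*D* = 1) or 0.084 (*D* = 2) at half agreement, and 0.093 or 0.268 if all of a child's events share one grade.

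**4. The child as unit.** Chi-square on children with at least one event gives 0.046 to 0.053 in all twelve scenarios of steps 1 and 2. The simulation standard error is √(0.05 × 0.95/10,000) = 0.002, so this is the nominal 5%.

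**5. The severity grade.** Protocol 10.2.1 has four levels and Table 25 has three. Protocol 10.2.2 makes a life-threatening event serious by definition, so it would be counted under Serious = Yes and its severity would show in the Table 24 listing, but it has no severity row in Table 25.

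**The case against.** The only safety test that SAP 4.2.6 describes in words is on the proportion of subjects with serious events, which uses the child as unit; protocol 12.4 says the same. The Table 25 specification says how a test can be obtained and names no unit. Its reference to numbers of events points to Table 24B, which has no labelled p-value column. SAP 4.2.6 cites a Table 25A for the tests; no shell has that number, but by analogy with Table 24A it could mean the table by subjects. The severity and outcome rows could be filled with one worst value per child without changing the layout.

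Events may also be few. The Table 25 title restricts it to events possibly or probably related to study drug, and protocol 16.2 expects relatively few events or medications to code in otherwise healthy children. With an assumed 20 affected children per arm, 1.1 to 1.2 events each, within-child correlation 0.3 to 0.7 and Fisher's test for small cells, an event-level test of a category row rejects in only 2% to 8% of null trials. With 150 affected children per arm (150/336, or 45%), 1.5 to 3 events each and the same correlations, it rejects in 8% to 24%. That second setting looks heavy for this trial.

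Much of this stands. It rules out saying that the whole table is wrong, and it rules out a single headline figure. It does not remove the point. SAP 4.2.6 does say event numbers will be compared, Table 25 has an event-total row beside an unqualified p-value column, and the only method offered assumes independence.

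**Conclusion.** The point holds in limited form. The plan calls for a comparison of event counts, supplies only a test for independent units, and does not say which rows that test serves. P-values for event totals can therefore be too small. The same applies to severity, relationship and outcome, but only if those rows are counted by event. For event totals the error is nil if events are independent, and the false-positive rate is about 11%, 17% and 26% at assumed variance/mean ratios of 1.5, 2 and 3. Using children as the denominator adds to it.

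Three stronger readings are tempting and are not supported. A reader might infer that every p-value in Table 25 is too small; the child-level rows and the serious-event proportion test are valid. A reader might infer that the trial is set to claim falsely that fewer antibiotic days cause fewer or milder events; no such claim is planned, and neither the primary analysis nor the halting rules use these p-values. A reader might infer that life-threatening events would vanish from the output; they would appear under Serious = Yes and in the listing, and lack only a severity row.

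**What to change.** In SAP 4.2.6 and the Table 25 specification:

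- State that p-values are given only for rows in which each child is counted once: any adverse event, worst severity, any related event, any serious event, any unresolved event. Chi-square or Fisher is then appropriate.
- Report total events by arm without a p-value, or compare them with a method that allows for repeated events in a child, such as a negative binomial model.
- Add a life-threatening row to the severity block to match protocol 10.2.1.
- Correct the reference to Table 25A so that it points to an existing shell.

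The cost is edits to one shell and a sentence or two of SAP text. No new data are needed, since severity and relationship are already recorded for each event.

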7.2 Consort diagram

Figure 1: Consort Diagram
